#### **4.1 Study Visit**

Upon patient entry into this study we will:

- Review inclusion/exclusion criteria
- Obtain written informed consent in a private setting.
- Perform CEUS exam
- Department policies concerning COVID19 safety will be followed

#### **4.2 Image interpretation**

Images will be assessed by the Principal Investigator (see Primary Endpoint in Section 5.1). Results of image interpretation will not be reported nor impact clinical management. No personnel beyond the PI and study personnel will have access to the master list with identifiable findings.

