with empirical formula C38H74 NaO10P, has a molecular weight of 745.

---

Study Design	Cross-sectional observational study.
Subject Population	Inclusion Criteria
key criteria for Inclusion and Exclusion:	
 
1. Patient (male/female) hospitalized at CHOP.
 
2. Patient 17 years of age or younger.
 
3. Diagnosis of COVID-19 or high clinical suspicion for COVID-19 despite negative tests (according to the definition of probable case by the ECDC).
 
4. Patients have evidence of cardiovascular compromise, myocardial injury, acute kidney injury, and/or new-onset neurological symptoms.
 
5. Parental/guardian permission (informed consent)
 

	Exclusion Criteria
	
 
1. Medical history of Lumason hypersensitivity
 

Number of Subjects	Total recruitment: 30 patients with confirmed or probable diagnosis of COVID-19.
Study Duration	CEUS has a total duration of approximately 15 minutes including contrast agent injection and image completion.
Study Visit	Subjects will be imaged at bedside at CHOP for approximately 15 minutes.
Efficacy Evaluations	CEUS scans of diagnostic quality, qualitative/quantitative evaluation of microvascular perfusion of heart, kidneys and/or brain in COVID-19 patients, correlation between CEUS and clinical outcomes of COVID-19.
Pharmacokinetic Evaluations	There are no pharmacokinetic evaluations.
Safety Evaluations	All subjects receiving at least one injection of investigational drug will be included in the safety analysis. The frequencies of AEs by type, severity, and temporal relationship to the CEUS scan will be summarized. SAEs (if any) will be described in detail.
Statistical and Analytic Plan	
This is a pilot study with a projected recruitment of 30 children with COVID-19.
 
See Section 5.3 for further detail.

---

---

**DATA AND SAFETY MONITORING PLAN** The safety monitoring for this study is the primary responsibility of the study team. Regular meetings to discuss the outcomes of the study, and of the safety events, will be conducted by the study team. The occurrence of adverse events, serious adverse events and unanticipated events will be reported by the study team in accordance with federal and institutional guidelines, as outlined in Section 7 of this clinical study.

---

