## 4 STUDY PROCEDURES

Screening will be performed via medical chart review and/or clinical referral of pediatric subjects at the Children's Hospital of Philadelphia. Subjects who fulfill eligibility criteria will be included.

CEUS scan will be performed by CHOP study team members and/or dedicated research ultrasonographers. Subjects will undergo one CEUS exam. The dosing plan will be weight-adjusted, based on a dose of 0.03 mL/kg. Up to two injections per study will be performed as per product label/FDA guidelines. Subjects' and personnel safety will be handled according to clinical protocol for COVID-19.

Organ perfusion will be evaluated in the heart, kidneys and/or brain, provided there is evidence of cardiovascular compromise, myocardial injury, acute kidney injury, and new-onset neurological symptoms. Brain ultrasound will occur if there are new-onset neurological symptoms. We will use a low energy approach to minimize the risk of thermal injury or disruption of the blood-brain-barrier (mechanical index < 0.2 is safe).

Analysis of CEUS imaging by the Principal Investigator will be performed, in addition to medical chart review for clinical outcomes (exploratory analysis).

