### 5.3 Sample Size and Statistical Analysis Plan

We will enroll 30 subjects (15 male/15 female) in this pilot study. As part of clinical care, CHOP Radiology also performs approximately 4-5 contrast-enhanced ultrasound cases in a given day, which is higher in volume than any other children's hospital in the country.

---

A sample size of 30 should provide reasonable estimates of the perfusion metrics. For example, a sample size of 30 participants produces a two-sided 95% CI with a width equal to 0.3 when the estimated proportion is as small as 0.3 (95% CI=0.1, 0.5). Also, a two-sided 95% CI with a width equal 0.6 when the estimate of Pearson's product-moment correlation is 0.4 (95% CI= 0.05, 0.7).

Based on microangiopathy/ischemia observed in COVID-19 patients (9-11), we expect our cohort to display delayed perfusion, hypoperfusion or no perfusion of the myocardium, kidneys, and/or brain. Results of the myocardial, renal and brain perfusion will be assessed by two experienced researchers in the field of CEUS and report it qualitatively as either normal or abnormal. In case of diagnosis disagreement between the two raters, a third experienced researcher will confirm the correct diagnosis. Hence, the proportion and frequency of myocardial, renal, and/or brain perfusion abnormalities will be documented. As additional primary analysis, we will also assess quantitative CEUS and derive time-to-peak (TTP) and wash-in area under the curve (WiAUC).

Demographic characteristics and descriptive statistics (such as measures of frequency, central tendency, dispersion, and position) will be summarized for the sample and by male and female sex. The percentage of COVID-19 patients with an abnormal clinical exam will be computed. Time intensity curve analysis will provide further details on the nature of perfusion abnormalities. The following presents the variable names, output, and the reported statistics for the primary and secondary aims.

	Measured Variables	Output and statistics
Primary Analysis	Perfusion defect (hypo- or absent perfusion)	Proportion of COVID-19 patients with perfusion defect
Primary Analysis	Perfusion quantified using time-to-peak (TTP) and wash-in area under the curve (WiAUC) from the time-intensity curve of contrast signal	Summary statistics for TTP and WiAUC, for e.g. mean, standard deviation, 95% CI
Secondary Analysis	Clinical outcomes from chart review etc.	Correlation of CEUS metrics to clinical outcomes

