## 8 STUDY ADMINISTRATION

### 8.1 Data Collection and Management

Confidentiality: All subjects will be assigned a number unrelated to their medical record number or name and this will be kept in a master list. The master list will contain patient identifiers and a link to the research-specific code. The master list will be kept in the PI and Study coordinator's password protected computer at CHOP, on the secure storage network

on the secure Hospital server. Co-investigators will have access to patient identifier's (name, MRN) during the optimization phase of their study. When the optimization finishes, or the article is published all the identification will be erased and only kept in the master list at the PI and Study coordinator computer. The collection of data from EPIC, ChartMaxx, and/or iSite Radiology will be using the MRN or name. Data will only be transferred between members of the study team; no identifiable data will be shared with non-CHOP or CHOP individuals who are not on the study team.

**Security:** All files (master list and coded data) will be password protected and will be stored on a password protected computer at CHOP, or in a password-protected hard drive. The hard drive will meet CHOP IT standards for encryption and password protection. The only way we will use to transfer internal information will be [send secure] emails using the study [contact] accounts. Access to the medical records and diagnostic studies to collect the data requires patient identifiers such as: medical record number and name. Without these, we would be unable to retrieve and review any information previously collected. For that reason, during the data collection process, we could send identifiable data using the protected CHOP-email.

Image data will be given a unique code and will have no information that can identify the subjects. Information that can identify subjects or image data may be kept in the master list at the PI and study coordinator's computer. Only the study team (co-investigators, PI, study coordinator, research assistants, etc) will be able to see information that can identify the subjects. If the subject leaves the study, he/she can ask to have the image data collected to be removed or destroyed. Imaging data will be archived to permanent storage media at the CHOP secure PACS system.

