The study team will share unique research data accrued from this pilot clinical trial to enhance the value and further the advancement of research. The study team will make available such data after study completion and the data will only be provided to those investigators who agree to adhere to a signed research data use agreement. The data and associated documentation will be available to users only under a data-sharing agreement that provides for: (1) a commitment to using the data only for research purposes; (2) a commitment to securing the data using appropriate computer technology; and (3) a commitment to destroying or returning the data after analyses are completed. The data obtained will be periodically reviewed (once every month) by the study team for discussion and improvement as well as planning for dissemination of results to the scientific community.

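### Section 4.2 gives the primary-endpoint read to the Principal Investigator and section 5.3 gives it to two raters plus a third; the PI's role is not stated, and no text masks readers or makes reads final before outcomes are reviewed

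*Combined protocol and SAP*

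**What the plan says.** Three places in the combined protocol and SAP say who evaluates the images.

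- Section 4.2: "Images will be assessed by the Principal Investigator (see Primary Endpoint in Section 5.1". Section 5.1 is the proportion of patients with normal perfusion versus areas of hypoperfusion.
- Section 4: "Analysis of CEUS imaging by the Principal Investigator will be performed, in addition to medical chart review for clinical outcomes (exploratory analysis". No one is named for the chart review, and no order is set between the two tasks.
- Section 5.3: perfusion results "will be assessed by two experienced researchers in the field of CEUS and report it qualitatively as either normal or abnormal". It adds: "In case of diagnosis disagreement between the two raters, a third experienced researcher will confirm the correct diagnosis".

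For the statistical plan the synopsis says "See Section 5.3 for further detail", which makes section 5.3 the natural governing text. No passage says that it overrides sections 4 and 4.2.

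On identifiers, section 8.1 gives image data a code without identifying information and leaves the master list with the PI and the study coordinator. Co-investigators have names and record numbers for a period, which ends as follows: "When the optimization finishes, or the article is published all the identification will be erased and only kept in the master list".

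Section 5.2 counts death to 28 days and mechanical ventilation to 14 days after imaging, and also lists myocardial infarction, stroke and renal failure. Sections 3.1 and 5.3 correlate CEUS results with clinical outcomes; section 3.1 labels this exploratory.

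**The concern.** The primary endpoint is a visual, two-category judgement. As the text stands, one team could follow section 4.2 with a single read by the PI and another could follow section 5.3 with two reads and a tie-breaker. Both could claim to have followed the plan.

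The second issue is what a reader knows, and when. A reader who knows how ill a child is, or how the child fared, may call a borderline image differently. If reads follow outcomes in this way, part of any association between CEUS and outcome comes from the reading itself. The primary proportion could also shift, and this single-group study has no comparison group in which a shifted reading threshold would show. Section 1.1 intends these estimates and their confidence intervals for designing a future trial, so an error here would carry forward.

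**Working it through.** This is mainly a check of text against text.

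**1. Is it the same read?** Section 4.2 points to section 5.1, whose endpoint is the qualitative proportion. Section 5.3 describes that same normal/abnormal call and gives it to two raters plus a third. Section 4 differs: it gives the PI CEUS analysis without tying it to the primary endpoint. It could mean the time-to-peak and wash-in area analysis, for which section 5.3 names no one. The overlap therefore rests on sections 4.2 and 5.3.

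**2. Can the two be reconciled?** Yes, for example if the PI is one of the two raters or the third reader. The plan states neither. This is an unreconciled assignment.

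**3. Is any reader masked?** I found no passage that withholds clinical status, laboratory values, outcomes or the other rater's call. Speaking of disagreement between two raters implies two separate calls but does not require them to be made independently. Section 8.1 does not say that readers see only coded images, and the PI, a named reader, holds the key.

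**4. Is the read fixed before outcomes are known?** Outcome windows close 14 and 28 days after imaging. No deadline or lock is set for the read, so it could come before or after those dates, or be revised after them.

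**5. Does section 4.2 close the gap by keeping results out of care?** Only in one direction. Image results cannot then influence outcomes through treatment, but knowledge of outcomes can still influence the read.

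**6. Scale.** Inputs from section 5.3: n = 30, illustrative proportion 0.3 with a stated interval of 0.1 to 0.5 and width 0.3, and illustrative correlation 0.4 with a stated interval of 0.05 to 0.7.

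- Proportion (Wald): 0.3 ± 1.96 × √(0.3 × 0.7 / 30) = 0.3 ± 0.164, or 0.136 to 0.464, width 0.328. This matches the plan after rounding to one decimal.
- Correlation (Fisher z, SE 1/√27): 0.046 to 0.665. This also matches after rounding.
- One changed read: 1/30 = 0.033, about a tenth of the interval width (0.033 / 0.328 = 0.10).

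Both intervals describe sampling error only and make no allowance for reads that depend on outcome. The documents give no reader accuracy or agreement figures, so the number of reads that might change cannot be estimated. The 0.033 is a unit of scale and does not estimate bias.

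**The case against.** The case on the other side has four parts.

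- **The PI may do only the quantitative analysis.** This stands for section 4. It fits section 4.2 poorly, because that section refers to the primary endpoint. A reader might infer that the sections flatly contradict each other; the documents do not support that, since the PI could be one of the section 5.3 readers.
- **Section 5.3 governs, so only wording needs aligning.** This largely stands for reader assignment. It does not touch masking or timing, on which section 5.3 is silent.
- **The stakes are modest.** This is a single-group pilot, the outcome correlation is exploratory, and image results do not affect care. Two raters and a tie-breaker limit one reader's idiosyncrasy, and coding gives some protection for any reader without the key. All of this stands and lowers the weight of the point. It does not remove a bias shared by all readers, or one in a read by the PI alone.
- **Masking can only be partial.** Organ compromise is an entry criterion (section 3.3.1), and study team members screen charts and may scan at the bedside (sections 3.1.1 and 4). A reader may already know current severity. This stands, and it is why the timing of the read matters most.

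A reader might also infer that the readers will in fact see outcomes. The synopsis says "Regular meetings to discuss the outcomes of the study, and of the safety events, will be conducted by the study team", and section 8.1 says "The data obtained will be periodically reviewed (once every month) by the study team for discussion and improvement". The first sits in the safety monitoring plan. The second closes a paragraph on data sharing and goes on to dissemination of results. Neither says that outcomes of individual children are shown to readers. They show that nothing prohibits exposure, not that it occurs.

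**Conclusion.** The point holds as a gap in the text. Sections 4.2 and 5.3 assign the same primary-endpoint call differently, the PI's role is unstated, and nothing masks readers or fixes reads before outcomes are reviewed. A team following the plan as written could make a single, unmasked PI read with the 14- and 28-day outcomes already known.

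The consequence is possible but not demonstrated. It bears most on the exploratory correlation, on the assumption that the normal/abnormal read is among the CEUS findings correlated with outcomes; sections 3.1 and 5.3 do not list which ones are. It bears less on the primary proportion. Section 5.3 expects abnormal perfusion in this cohort, and a reader might infer from this that the proportion will be too high. The documents do not support that: neither the direction nor the size of any bias can be derived from them. The change is a cheap improvement worth making before images are read.

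**What to change.** - State that the two-plus-one procedure in section 5.3 governs the primary read, align sections 4 and 4.2 with it, and say whether the PI is a rater, the third reader or neither. If the PI's part is the quantitative analysis, say so.
- Have each reader, including the third, read coded images separately and without chart, laboratory or outcome data.
- Date and lock each read before that child's outcomes are abstracted or linked. The coordinator, who already holds the master list, does the linking.
- Keep an exception for PI access to identifiers and clinical data for safety reporting (sections 7.5 and 8.3.1).
- Where staffing allows, give reads to people who did not screen or scan that child; otherwise record that they did.

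**Cost.** Mainly wording: the readers, coding and coordinator are already planned, and no scan is added. Some screening, reading and abstraction tasks would have to be reassigned. The documents give no team size, so full separation may not be possible for every child. Masking to current severity will be incomplete for the reasons given above, but the lock still protects the read against knowledge of later outcomes.

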##### **4.2.1 Follow-up**

The medical chart of subjects who underwent CEUS examination will be reviewed to assess clinical outcomes (see Secondary Endpoint in Section 5.2).

#### **4.3 Subject Completion/Withdrawal**

Subjects may withdraw from the study at any time without prejudice to their care. They may also be discontinued from the study if they become anxious during this research examination. No sedation will be given. The Investigator may also withdraw subjects who violate the study plan, or to protect the subject for reasons of safety or for administrative reasons. It will be documented whether each subject completes the research study. If the Investigator becomes aware of any serious, related adverse events after the subject completes or withdraws from the study, they will be recorded in the source documents.

---

## 4.4 Data variables

### 4.4.1 EPIC

- Name
- MRN
- Date of birth
- Sex
- Chief complaint
- Symptoms
- Duration of symptoms
- Hospital stay
- Medications being used during hospitalization
- Laboratory tests during hospitalization
- Presence of myocardial infarction during hospitalization
- Presence of stroke during hospitalization
- Presence of renal failure during hospitalization
- Time to recovery
- Need for oxygen
- Need for mechanical ventilation
- Vascular complications

### 4.4.2 PACS

- Accession number
- All images obtained using CEUS

## 5 STATISTICAL CONSIDERATIONS

### 5.1 Primary Endpoint

1. Estimate the proportion of patients with normal perfusion versus area(s) of hypoperfusion in heart, kidneys and/or brain.

### 5.2 Secondary Endpoints

1. Evaluate heart, kidneys and/or brain perfusion using time to peak (TTP) and wash-in area under the curve (WiAUC).
2. Death within 28 days of imaging or mechanical ventilation within 14 days of imaging as reported in the medical chart.
3. Myocardial infarction, stroke, or renal failure as reported in the medical chart.

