## 3.2 Study Duration, Enrollment and Number of Sites

### 3.2.1 Duration of Study Participation

Study participation will occur during the inpatient stay. Study duration per participant will include telephone screening lasting approximately 5-10 minutes to confirm eligibility for the study and CEUS safety.

The CEUS exam will last approximately 15 minutes but no more than one hour. Only one CEUS scan will be performed per patient.

Clinical outcomes during hospitalization will be documented via chart review. No outpatient follow-up will be performed.

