## 3.3 Study Population

### 3.3.1 Inclusion criteria

1. Patient (male/female) hospitalized at CHOP.
2. Patient 17 years of age or younger.
3. Diagnosis of COVID-19 or high clinical suspicion for COVID-19 despite negative tests (according to the definition of probable case by the ECDC).
4. Patient has evidence of cardiovascular compromise, myocardial injury, acute kidney injury, and/or new-onset neurological symptoms).
5. Parental/guardian permission (informed consent)

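### Section 5.2 scores renal failure by chart wording, so children with the same kidney course can be scored differently, which can bias the exploratory CEUS correlation in either direction

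*Combined protocol and SAP*

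**What the plan says.** All references are to the combined protocol and SAP.

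- **Outcome.** Section 5.2, item 3: "Myocardial infarction, stroke, or renal failure as reported in the medical chart". Section 4.4.1 collects it as a yes/no item: "Presence of renal failure during hospitalization". No section gives a creatinine, urine-output, staging or dialysis criterion, a baseline value, or adjudication.
- **Timing.** Item 2 of Section 5.2 counts from the scan: "Death within 28 days of imaging or mechanical ventilation within 14 days of imaging as reported in the medical chart". Item 3 has no such window. Section 3.2.1 says "Clinical outcomes during hospitalization will be documented via chart review", with no outpatient follow-up.
- **Entry.** Section 3.3.1, criterion 4: "Patient has evidence of cardiovascular compromise, myocardial injury, acute kidney injury, and/or new-onset neurological symptoms". Acute kidney injury is thus one of four alternative routes in, and it is not defined either.
- **Laboratory data.** Section 4.4.1 also lists "Laboratory tests during hospitalization", without analytes or frequency and without a link to the renal item.
- **Use.** The table in Section 5.3 gives the secondary analysis as "Correlation of CEUS metrics to clinical outcomes". Sections 1.1, 3.1 and 4 call this analysis exploratory.

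**The concern.** The documents draw no line between the acute kidney injury that can admit a child and the renal failure that counts as an outcome. Which term reaches the chart depends on the clinician who writes the note. Laboratory tests are already on the data list, so one rule could be applied to every child, but Section 5.2 states the chart label.

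Two things follow for the CEUS correlation. First, uneven labelling is misclassification of the outcome. Second, because item 3 has no start point, kidney injury already present at the scan can be counted as an outcome that the scan is then said to correlate with.

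Section 1.1 wants this pilot to supply figures for a later trial and names renal failure among the complications that a perfusion biomarker might predict. A renal event rate or correlation built on undefined wording is hard to carry into that trial.

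**Working it through.** **Inputs from the documents.** n = 30, and a planning correlation of 0.4 with a two-sided 95% CI of 0.05 to 0.7 and a width of 0.6 (Section 5.3).

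**Inputs assumed.** The sensitivity (Se) and specificity (Sp) of the chart label, and the true prevalence (p) of renal failure. The documents give none of these, so a range is shown.

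**1. The plan's own figure.** Fisher z interval: tanh(atanh(r) ± 1.96/√(n − 3)). With r = 0.4 and n = 30 this is 0.046 to 0.665, width 0.618. It agrees with Section 5.3 after rounding.

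**2. Label error unrelated to CEUS.** Let q = p·Se + (1 − p)(1 − Sp) be the proportion labelled. The correlation between label and true state is

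φ = (Se + Sp − 1) × √[p(1 − p) / (q(1 − q))],

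and the observed correlation is r × φ.

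Example with p = 0.20, Se = 0.6, Sp = 0.95:
- q = 0.12 + 0.04 = 0.16
- φ = 0.55 × √(0.16/0.1344) = 0.60
- observed r = 0.40 × 0.60 = 0.24, with n = 30 interval −0.13 to 0.55

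| p | Se / Sp | φ | Observed r | 95% CI, n = 30 |
|---|---|---|---|---|
| any | 1 / 1 | 1.00 | 0.40 | 0.05 to 0.66 |
| 0.3 | 0.9 / 0.95 | 0.85 | 0.34 | −0.02 to 0.62 |
| 0.3 | 0.8 / 0.95 | 0.77 | 0.31 | −0.06 to 0.60 |
| 0.2 | 0.6 / 0.95 | 0.60 | 0.24 | −0.13 to 0.55 |
| 0.1 | 0.6 / 0.90 | 0.42 | 0.17 | −0.20 to 0.50 |

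Over Se 0.6 to 0.8, Sp 0.90 to 0.95 and p 10% to 30%, the observed value runs from 0.17 to 0.31.

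**3. Label error related to CEUS.** Assume a binary CEUS reading and a binary true outcome, each with prevalence 0.3 and φ = 0.40. The share with both is 0.09 + 0.4 × 0.21 = 0.174. The two discordant cells are 0.126 each, and the share with neither is 0.574. Let Se/Sp be 0.9/0.8 in CEUS-abnormal children and 0.6/0.95 in the others.
- Labelled and abnormal: 0.174 × 0.9 + 0.126 × 0.2 = 0.1818
- Labelled and normal: 0.126 × 0.6 + 0.574 × 0.05 = 0.1043
- Labelled in total: 0.2861
- Observed φ = (0.1818 − 0.3 × 0.2861) / √(0.21 × 0.2861 × 0.7139) = 0.46

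With the two Se/Sp pairs exchanged, the observed φ is 0.04. With 0.7/0.9 in both groups it is 0.24. The direction therefore depends on how the error relates to CEUS.

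**4. Fewer kidney scans.** Section 4 ties imaging to organ evidence ("Organ perfusion will be evaluated in the heart, kidneys and/or brain, provided there is evidence of cardiovascular compromise, myocardial injury, acute kidney injury"), so fewer than 30 children may have a kidney scan. At r = 0.40 with no label error, the interval is −0.05 to 0.72 for n = 20 and −0.14 to 0.76 for n = 15.

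**The case against.** **The size rests on assumptions, and an interval that reaches zero says little.** This stands. At n = 30 an interval excludes zero only if r exceeds tanh(1.96/√27) = 0.36, so the undiluted 0.40 has almost no margin. The useful result is the change in the estimate, and it is illustrative only. A laboratory rule would have its own error, so 0.40 is the most that could be recovered. The plan is also descriptive and does not rest on significance.

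**Dilution is not certain.** This stands too. A reader might infer that chart labelling must weaken the correlation. Section 4.2 keeps the CEUS result out of clinical care, which favours unrelated error in the clinicians' wording. However, Section 4 names the investigator's image analysis and the chart review together, and blinding of the person who abstracts the chart is not stated. Step 3 shows that the error can go either way.

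**The text should not be read too strongly.** Four inferences are tempting, and the documents do not support them:
- That a creatinine series is guaranteed. Section 4.4.1 names no analyte or frequency, and Section 3.1.1 schedules laboratory evaluation only at the CEUS encounter.
- That laboratory values are excluded. Chart review could include them; what is missing is a rule that says how.
- That every child enters with kidney injury. It is one of four and/or conditions.
- That a separate analysis of kidney CEUS against renal failure is specified. Item 3 lists three events together, and Section 5.3 speaks only of clinical outcomes in general.

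**What remains.** The stated scoring method is a label with no boundary from an entry condition and no start point, although a more uniform source is already on the data list.

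**Conclusion.** The point holds as a minor improvement to an exploratory secondary analysis. Scoring renal failure by chart wording lets the same kidney course count as an outcome in one child and not in another, and the lack of a start point lets injury present at imaging count as well.

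The effect on the renal CEUS correlation is conditional. If labelling error is unrelated to CEUS, a true 0.40 would appear as about 0.24 in the worked example and as 0.17 to 0.31 over the assumed range. If CEUS-abnormal children are labelled more readily, it can rise, to 0.46 in the example. Counting injury already present at the scan could also raise it; no figure is put on that. Sensitivity, specificity and prevalence are all assumed, and the Fisher interval is an approximation for a binary outcome. The primary proportion of children with a perfusion defect is not affected.

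**What to change.** In Section 5.2, derive the renal outcome for every child from the available creatinine values and any recorded dialysis, using one prespecified published staging rule (KDIGO is one example). State:

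- the baseline value, such as the last one at or before the scan;
- the stage that counts as renal failure;
- a window that starts at imaging.

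Report kidney injury present at the scan separately from new or worsening injury. Use the post-scan peak stage, as an ordinal variable, for the kidney CEUS correlation. Keep the chart label as a sensitivity analysis.

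The cost is SAP wording and a small derivation. The rule depends on values from routine care, so children without enough creatinine values must be reported as not classifiable by the rule, with their chart label shown only in the sensitivity analysis. Substituting the label for them in the main result would bring back the uneven scoring. If many children are not classifiable, the renal correlation will rest on a smaller number, which should be stated beside it.
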